### **6.3.2 Study Methodology/Procedures**

Seventeen patients who are already using Intrathecal therapy and PTM dose will be randomized in a 1:1 ratio by a computer generated randomization table to receive one of two treatments. At patient’s regular scheduled appointment for pump refill, the residual intrathecal medication volume will be removed from the pump and half of the patients will be allocated to receive the opioid alone whereas the other half will receive the same solution containing the opioid with bupivacaine.

At each of the first two visits following signing of informed consent Patient should be refilled in the IDD pumps with a 10 mL solution containing either the usual intrathecal medications (solution A or Solution B—coded by pharmacy) including bupivacaine with the opioid (same intrathecal solution) or their usual intrathecal solution with the same opioid concentration but without bupivacaine. Taking away bupivacaine from the intrathecal solution does not result in withdrawal. The investigational pharmacy at UHCMC would be the only party who knows whether the patients are receiving solution A or solution B. No changes will be recorded in pump programming with respect to the opioid. However, upon each of the two first visits after consent, when the patients are refilled with 10 ml of solution A or solution B, the pump will be programmed with the same concentration of the opioid and bupivacaine labeled at 29 mg/ml at the first visit and 30 mg/ml at the second visit. Changing the solution at the first visit to a label of bupivacaine 29 mg/ml will not affect the delivery of the opioid or bupivacaine (if the solution has bupivacaine) as the only (and primary) driver for amount delivered is the opioid which will not change in concentration or dose throughout the study. However, labeling the bupivacaine with 29 mg/ml (a concentration not used and different from previous bupivacaine concentration) will prompt the decision algorithm to request a “bridge bolus”—namely, a calculation of how long it would take for the new solution to get through the dead space in the pump and catheter to get to the catheter tip. Upon changing the solution in the pump, it may take about a day or so for the new medication to enter the intrathecal space because of dead space. The exact duration is dependent on the patient’s initial rate (ml/day) the length of the catheter in the patient; thus would vary from patient to patient. The dead space in the Medtronic SynchroMed II pump is comprised of the internal tubing within the pump (0.199 ml) + external catheter tubing extending from the pump to the Intrathecal space (usually about 0.1 to 0.15 ml). This amount is calculated at pump change and is usually on the order of one day, but varies and the pump programmer will calculate the exact date when the bridge bolus is completely delivered. Importantly, during the bridge bolus, the patients will not be able to self-administer PTM boluses. Many patients may be used to this with solution changes. When the bridge bolus is completely administered, usually after a day or so, the

University Hospitals Case Medical Center  
 Department of Anesthesiology  
 Division of Pain Medicine  
 Study title: “*Effectiveness of Self-Administered Boluses of Intrathecal Bupivacaine in Patients with Chronic Non-Cancer Pain Implanted with IDDS: A Double Blind Randomized Study*”  
 Principal Investigator: [name] [name]

patient will be able to self-administer PTM doses. When doing so, the patients will be receiving either opioid + bupivacaine (exactly similar to baseline) or opioid alone (similar

to baseline but without bupivacaine). Hence, patients will continue to have access to PRN (as necessary) analgesia with self-administered PTM doses. As patients will be kept on solution A or solution B for a maximum of one week each, the maximal duration without bupivacaine in the intrathecal bolus would be one week.

The patients will be provided with a paper diary that will be attached by Velcro to the PTM remote device which will act as a reminder for patients to record pain scores prior to the PTM bolus. The patients will also record the lowest pain scores within the first 30 minutes after a PTM bolus. Only the first 3 successful PTM boluses per day will be recorded and tracked by the study. The patients will also record the average NRS score and GPE score daily. Reminders to complete the diary will also be provided to patients via phone, email or text message.

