**Protocol Title:**

“Randomized, double blind, cross over study comparing effectiveness of traditional opioids versus opioids in admixture with bupivacaine upon self-administration of boluses via a Personal Therapy Manager (PTM) in Intrathecal pump”.

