**ABSTRACT**

**2.1 Purpose:**

To determine whether the local anesthetic bupivacaine delivered intrathecally in small doses via PTM self-administered boluses significantly improves the breakthrough pain and functional status of patients with chronic intractable pain who are managed with an intrathecal drug delivery system.

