**3. OBJECTIVES AND RATIONALE**

The objective of this project is to conduct a randomized, double-blind, effectiveness study to determine whether intrathecal delivery of bupivacaine via self-administered boluses significantly improves breakthrough pain and functional status in patients with chronic, non-cancer pain who are managed with an implanted intrathecal drug delivery system (IDDS). This is important because some practitioners choose only a mono therapy (i.e. opioid) in the intrathecal solution without bupivacaine. This would delay pain relief without the near instant relief bupivacaine has been reported to provide after a PTM bolus.

University Hospitals Case Medical Center

Department of Anesthesiology

Division of Pain Medicine

Study title: *“Effectiveness of Self-Administered Boluses of Intrathecal Bupivacaine in Patients with Chronic Non-Cancer Pain Implanted with IDDS: A Double Blind Randomized Study”*

Principal Investigator: [name] [name]

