### **6.2 Selection of Subjects**

#### **6.2.1 Type of the Subject Population**

Patients with intractable chronic pain being managed with an intrathecal drug delivery system programmed with a continuous infusion as well as a self-administered bolus (PTM) for breakthrough pain who have an opioid as well as bupivacaine in the intrathecal solution and have been stable on their current settings for at least 3 months.

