### **6.3 Study Design and Methodology**

#### **6.3.1 Study Design**

This is a randomized, double-blind, effectiveness study looking at self-administered boluses of an opioid with and without bupivacaine via a Personal Therapy Manager (PTM) in patients with an intrathecal drug delivery system to assess the effect of bupivacaine administered by PTM on pain scores and functional status in patients with breakthrough pain. Patients in group I will receive a refill of a 10 mL solution “A” containing their usual intrathecal opioid and including bupivacaine. Patients in group II will receive a refill of a 10 mL solution “B” containing their usual intrathecal opioid without bupivacaine. Both groups will be kept on solution A and on solution B for a maximum of one week each after which they will cross over to the other solution for one week and then exit the study. The patients will then be returned to their baseline programming. Potential changes in programming to benefit patients may be undertaken as necessary—if existent—after unblinding. Primary outcome measures will include 0-10 numerical rating scale (NRS) or Visual Analogue Scale (VAS) both immediately before and within 30 minutes after a PTM bolus. Patients will be provided with a diary to record pain scores just before a PTM bolus and the lowest pain score within half an hour after a PTM bolus. Only 5 recording per day will be available on the diary—thus patients would record pain scores only before and after the first 5 PTM boluses. However, the scores before and after the first 3 successful PTM boluses would be the only ones considered. Successful PTM activations would be determined by review of the patient PTM diary and the internal log from the intrathecal drug delivery system. Each recording on the PTM diary would be time matched to the successful PTM activation code in the internal log. This will obviate any potential mis-administered bolus whereby the patient does not activate the bolus device appropriately.

University Hospitals Case Medical Center

Department of Anesthesiology

Division of Pain Medicine

Study title: *“Effectiveness of Self-Administered Boluses of Intrathecal Bupivacaine in Patients with Chronic Non-Cancer Pain Implanted with IDDS: A Double Blind Randomized Study”*

Principal Investigator: [name] [name]

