Secondary outcome measures will include average NRS pain scores for the day, functional capacity as evaluated by the Oswestry disability index (ODI) scores, number of boluses used, paresthetic sensation post bolus, and Global Perceived Effect.

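### The opioid-only week removes bupivacaine from the infusion as well as the boluses, so a difference in functional status (ODI) cannot be credited to PTM boluses as the objectives word it

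*Combined protocol and SAP*

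**What the plan says.** **Delivery.** Section 6.2.1 enrols patients whose pump is "programmed with a continuous infusion as well as a self-administered bolus (PTM) for breakthrough pain", with an opioid and bupivacaine in the solution.

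**Contrast.** Under 6.3.2 the pump is emptied and refilled with either the usual solution or "their usual intrathecal solution with the same opioid concentration but without bupivacaine". Section 6.3.4 allows no programming changes during the study. Section 6.5.2 describes the study as one of taking the local anaesthetic out of the pump solution.

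**Objectives.** Section 2.1 asks whether "bupivacaine delivered intrathecally in small doses via PTM self-administered boluses significantly improves the breakthrough pain and functional status". Section 3 asks whether "intrathecal delivery of bupivacaine via self-administered boluses significantly improves breakthrough pain and functional status". Section 6.3.1 sets out "to assess the effect of bupivacaine administered by PTM on pain scores and functional status".

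**Outcomes.** The primary (6.4.1, 6.4.4) is the average NRS change from before to within 30 minutes after a bolus, over the first three successful boluses a day. It is tied to the pump record: "Each recording on the PTM diary would be time matched to the successful PTM activation code in the internal log". ODI is collected at baseline and at the end of each one-week period (6.4.1). On the secondaries, 6.3.1 says "Secondary outcome measures will include average NRS pain scores for the day", and adds ODI, number of boluses, post-bolus paresthesia and Global Perceived Effect (GPE). The list in 6.4.1 has ODI, satisfaction, GPE and side effects.

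**The concern.** The objectives ask what bupivacaine does when given by bolus. The randomised contrast is bupivacaine by two routes against bupivacaine by neither. No period keeps it in one route and removes it from the other, so an outcome that reflects the whole week cannot say which route produced a difference.

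If the objectives are followed as written, a better ODI on bupivacaine would be reported as a benefit of PTM boluses. A clinician could then conclude that adding bupivacaine to boluses improves function, when the infusion may have contributed some or most of the difference.

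There is a second risk in the other direction. The primary is a change score. If bupivacaine lowers pain before and after a bolus by the same amount, the primary shows nothing, and a null result could be misread as no effect of bupivacaine at all.

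**Working it through.** **1. Which claim each outcome can support**

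| Outcome | Timed to a bolus? | What it estimates | Bolus wording in the objectives? |
|---|---|---|---|
| ODI | No, end of week | Whole solution | Yes: 2.1, 3, 6.3.1 |
| Daily average NRS | No | Whole solution | Only if the pain scores named in 6.3.1 are meant to cover it |
| GPE, satisfaction, number of boluses | No | Whole solution | No |
| Primary NRS change | Yes, log-matched | Bolus response on each solution, with the infusion also differing | Yes, as breakthrough pain |

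**2. The plan's sample size.** Inputs from 6.4.4: difference 2, within-patient SD 2, two-sided alpha 0.1, power 0.8.
- Normal approximation for a two-period crossover: N = 2 × [2 × (1.645 + 0.842)/2]² = 12.4, rounded up to 13.
- Exact t with N − 2 degrees of freedom: power 0.771 at N = 13 and 0.802 at N = 14. The stated 14 reproduces.
- Withdrawals: 14/(1 − 3/17) = 17.

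The calculation already uses the per-bolus change, so rewording the objectives does not alter it.

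**3. Is the infusion a negligible route?** The documents give no infusion rate. An approximate one follows from 6.3.2:
- Dead space: 0.199 + 0.10 = 0.299 ml to 0.199 + 0.15 = 0.349 ml.
- Cleared in about one day with PTM locked out: about 0.30 to 0.35 ml/day.
- Most that a 10 ml fill lasting seven days can deliver: 10/7 = 1.429 ml/day.
- Both routes deliver one solution, so share of volume equals share of bupivacaine: 0.299/1.429 = 20.9% to 0.349/1.429 = 24.4%.
- With a two-day bridge the rate halves: 10.5% to 12.2%.

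The share is higher if less than 10 ml is used and lower if the bridge takes longer.

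**4. What the change score can hide.** By identity, difference in post-bolus NRS = difference in pre-bolus NRS + difference in falls (opioid-only minus bupivacaine for the levels, bupivacaine minus opioid-only for the falls). With assumed scores of 5 falling to 3 on bupivacaine and 7 falling to 5 without it, 2 = 2 + 0. The primary difference is 0 while both levels differ by 2.

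A partial version, also on assumed values: suppose losing background bupivacaine raises pre-bolus NRS by s, and a bolus relieves a fraction r of that. The opioid-only fall then grows by r × s. For s = 0.5 and r = 0.1, a true difference of 2 appears as 2 − 0.05 = 1.95 (power 0.78 at N = 14). For s = 2 and r = 0.5 it appears as 2 − 1.0 = 1.0 (power 0.35). For s = 0 nothing changes. The documents give neither s nor r.

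**5. Precision of pre-bolus and post-bolus contrasts.** SE = 2 × √(2/14) = 0.756; t(12) = 2.179; 95% half-width = 1.65 points. This applies the SD of 2 to NRS levels, whereas 6.4.4 states it for the response variable, the change. If the change has SD 2 and the levels have equal SD with pre/post correlation ρ, the level SD is 2/√[2(1 − ρ)]: 1.41 at ρ = 0 (half-width 1.16) and 3.16 at ρ = 0.8 (half-width 2.60). These values of ρ are assumed.

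**The case against.** The strongest reply is that the plan is open about its contrast. The title compares opioid with an opioid–bupivacaine admixture, 6.3.1 and 6.3.2 describe the refill swap, 6.5.2 speaks of removal from the solution, and the rationale in section 3 concerns practitioners who leave bupivacaine out of the solution. ODI is a valid secondary outcome for that question, and the primary is timed to the bolus. All of this stands. It limits the defect to the wording of the objectives, but it does not remove it: no passage says that ODI is not bolus-specific.

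Four stronger readings are tempting, and the documents do not support them.

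- *The objectives credit daily average NRS to boluses.* Sections 2.1 and 3 name only breakthrough pain and functional status. Section 6.3.1 mentions pain scores, but goes on to define the primary scores as those just before and after a bolus.
- *The primary is free of the problem and can carry the bolus claim alone.* The infusion differs between periods during every bolus and may shift the pre-bolus score.
- *The primary is therefore invalid.* Log-matching and the 30-minute window make it the most bolus-specific efficacy measure available, and any shift may be zero.
- *The infusion carries at least a fifth of the bupivacaine.* Section 6.3.2 gives the bridge only as about a day, varying by patient. A share of dose is also not a share of effect.

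It is also fair to say that the added contrasts are imprecise against a 2-point target. They are descriptive for that reason.

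**Conclusion.** The concern holds for the attribution of functional status. ODI estimates the effect of the solution with versus without bupivacaine, by infusion and bolus together; crediting it to PTM boluses goes beyond what the design can show. The same limit applies to daily average NRS, GPE, satisfaction and number of boluses if anyone reads them as bolus effects.

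The primary remains usable as the bolus response on each solution, with the residual limit stated. A null primary should not be taken to mean that bupivacaine does nothing.

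The attribution point follows from the design and needs no figure. The infusion shares (roughly 20% or more, or roughly 10% or more) are illustrations resting on an approximate bridge time and a fully used 10 ml fill. The effect of the infusion on pre-bolus pain is unknown. This should be corrected before analysis; it does not call the treatment, the primary outcome or the sample size into question.

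**What to change.** Treatment, pump settings and sample size stay as they are.

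1. **Objectives (2.1, 3 and 6.3.1).** Add: *ODI and the other outcomes not timed to a bolus estimate the effect of the whole solution with versus without bupivacaine (infusion plus boluses) and are not attributed to the bolus alone. The primary outcome is the response to a bolus on each solution; the background infusion also differs between periods.*
2. **Analysis.** Beside the primary, report within-patient treatment contrasts with 95% confidence intervals for mean pre-bolus and mean post-bolus NRS, over the same first three successful boluses per day, labelled descriptive. State that a null primary is read together with these and with daily average NRS.
3. **Secondary outcomes.** Reconcile 6.3.1 with 6.4.1. Daily average NRS, number of boluses and post-bolus paresthesia are named only in 6.3.1; satisfaction is named only in 6.4.1.

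The cost is a short addition in three sections, one reconciled list and two summaries from diary data already collected. The downside is a narrower claim about boluses, and contrasts with a half-width of about ±1.65 points at 14 patients if an SD of 2 applies to NRS levels, which 6.4.4 does not state.

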**6.3.3 Collection of the Human Biological Specimens: N/A 6.3.4 Data Collection**

Randomization will be performed, patients will be recording data and baseline data will be collected during the first day or so after refilling with the study solution and the study data over the ensuing few days. No programming changes will be made during the study period. All participants will be kept on solution “A” and solution “B” for a maximum of one week each. All data will be obtained by a physician or member of the research staff.

**6.3.5 Study Time Line**

Assessment	4-8 wks before rx	1-2wks before	1 st refill Time 0	1 week later 2 nd refill	2 weeks	
Screening and Informed conse	x					
Randomization/data collection Questionnaire administration		x				
Initial study visit			x			
1st follow-up Data collection Including questionnaires				x		
2 nd follow up Data collection for 2 nd week					x	

**6.4.1 The primary endpoints (i.e., primary outcome variables) and the secondary endpoints, if any.**

University Hospitals Case Medical Center

Department of Anesthesiology

Division of Pain Medicine

Study title: “*Effectiveness of Self-Administered Boluses of Intrathecal Bupivacaine in Patients with Chronic Non-Cancer Pain Implanted with IDDS: A Double Blind Randomized Study*”

Principal Investigator: [name] [name]

The primary outcome variable will be the average change in the NRS for back pain scores between NRS scores before PTM bolus and NRS scores within 30 minutes after PTM bolus. Secondary outcome variables will be Oswestry disability score, satisfaction (categorical “positive” or negative”), the Global Perceived Effect score and side effects (medications). These variables will be recorded at baseline and during each follow-up visit. Global Perceived Effect and Oswestry questionnaires (as well as adverse effects) will be collected at baseline and at the end of each one-week study period.

#### **6.4.2-3 Data analysis, interim analysis and stopping rules**

Baseline data will be compared using analysis of variance (parametric or Kruskal Wallis ANOVA) for continuous or ordinal data and the chi square test for categorical data.

#### **6.4.4 Sample Size Estimation**

To estimate the sample size we based our calculation on the primary outcome which would be:

A. The difference of the average of the change in pain intensity score [Avg D NRS] of the first 3 successful PTM daily for 5 days [maximum 15 PTM boluses] between the Group I and Group II.

Specifically, from the literature and previous experience usually a change of 2 points in absolute pain score is considered minimally clinically significant. The provided parameters were: significance level (adjusted for sidedness) = 0.05, standard deviation within patients = 2, standard deviation of the difference = undefined, number of patients = undefined, power = 0.8, difference in means = 2.

The variable calculated was the total number of patients.

A total of 14 patients will enter this two-treatment crossover study. The probability is 80 percent that the study will detect a treatment difference at a two-sided 0.1 significance level, if the true difference between treatments is 2 points [NRS]. This is based on the assumption that the within-patient standard deviation of the response variable is 2.

Another 10-20% (or up to 3 patients should be factored in the sample size to account for normal withdrawals from the study. ***The final number of patient to be recruited for this study would be 17.*** These calculations were made using the sample size software.

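### Does the plan leave open whether the primary comparison is tested at two-sided 0.10 or two-sided 0.05?

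*Combined protocol and SAP*

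**What the plan says.** Section 6.4.4 bases the sample size on the primary outcome: the average change in NRS pain score around the first three successful boluses per day over five days, compared between the two solutions. The software inputs are "significance level (adjusted for sidedness) = 0.05, standard deviation within patients = 2" and "standard deviation of the difference = undefined, number of patients = undefined, power = 0.8, difference in means = 2". The result is 14 patients in a two-treatment crossover, described as follows: "The probability is 80 percent that the study will detect a treatment difference at a two-sided 0.1 significance level". The section repeats the assumption that "the within-patient standard deviation of the response variable is 2". It then notes that "up to 3 patients should be factored in the sample size to account for normal withdrawals from the study", which takes recruitment to 17.

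Section 6.4.2-3, headed as data analysis, interim analysis and stopping rules, is a single sentence: "Baseline data will be compared using analysis of variance (parametric or Kruskal Wallis ANOVA) for continuous or ordinal data", with a chi-square test for categorical data. It names neither a test nor a significance level for the primary comparison. Section 6.4.1 defines the primary variable without a decision rule. No significance level appears anywhere else in the document.

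**The concern.** Two alphas, 0.05 and 0.1, stand a few lines apart, and the first does not say that it applies per tail. A reader used to 5% tests could take it as two-sided 0.05 and see a contradiction. The section where the decision rule would normally be found does not settle the matter.

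The level can decide the verdict. A primary p-value between 0.05 and 0.10 is positive under one reading and negative under the other. If the level were picked after the data were seen, the two-sided false-positive rate could be 10% while 5% was claimed. And if the test were run at two-sided 0.05, the stated 80% power would not hold for the planned number of completers.

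**Working it through.** **Inputs, all from section 6.4.4.** Difference 2 NRS points; within-patient SD 2; power 0.8; two-sided level 0.1; 14 patients, raised to 17 for withdrawals. I take 14 as the planned number of completers. This is an inference: the text says 14 will enter, then adds 3 for withdrawals.

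**Formula.** In a two-period crossover the SD of a patient's paired difference is √2 × 2 = 2.83. With N completers, SE = 2.83/√N, the noncentrality is 2/SE, and power comes from the noncentral t distribution with N − 2 degrees of freedom.

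**Reproducing the plan's figure.** At N = 14, SE = 2.83/√14 = 0.756 and the noncentrality is 2/0.756 = 2.65. At two-sided 0.10, power is 77.1% for N = 13 and 80.2% for N = 14. So 14 is the smallest number reaching 80%, as stated.

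**Which level do the inputs imply?** Alternative readings were tried:

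- Two-sided 0.05, same SD: 18 completers needed (80.4%), not 14.
- Two-sided 0.10, normal approximation: ((1.645 + 0.842) × 2.83/2)² = 12.4, so 13.
- Two-sided 0.10, t with N − 1 degrees of freedom: 80.5% at N = 14.
- Two-sided 0.10, with 2 read as the SD of the difference: 97% at N = 14, far from 80%.

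The stated 14 and 80% fit a t calculation at two-sided 0.10. The input of 0.05 is the same level per tail: 0.10/2 = 0.05. The two statements agree.

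**Power under each level (N − 2 degrees of freedom).**

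| Completers | Two-sided 0.10 | Two-sided 0.05 |
|---|---|---|
| 14 | 80.2% | 68.1% |
| 17 | 87.2% | 77.8% |

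Simulation with 200,000 trials gave 80.1% and 67.9% for 14 patients (7 + 7), and 87.2% and 77.8% for 17 (9 + 8).

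**Size of the zone where the level matters.** With 14 completers and the assumed SD, the smallest significant observed difference is 1.35 points at two-sided 0.10 and 1.65 at two-sided 0.05. The chance that p falls between 0.05 and 0.10 is 80.2% − 68.1% = 12% if the true difference is 2 points, and 10% − 5% = 5% if there is none.

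**What 80% power at two-sided 0.05 would take.** It needs 18 completers. The protocol's allowance is an added 10–20%: 18 × 1.1 = 19.8, so 20; 18 × 1.2 = 21.6, so 22. That is 3 to 5 more recruits than 17.

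**The case for a change.** The strongest case for a change runs as follows. A level quoted in a power statement is a sizing assumption, not a decision rule. The decision rule belongs in the analysis section, which has none. An analyst could cite either number from 6.4.4. The 12% chance of an ambiguous p-value under the assumed effect is not negligible, and one sentence would remove it. Nor do the extra recruits rescue two-sided 0.05: even with all 17 completing, power is 77.8%.

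The arithmetic stands, and so does the observation that 6.4.2-3 says nothing about the primary comparison. The step from silence to a level left open is weaker. Section 6.4.4 ties its calculation to the primary outcome and gives one two-sided level. The 0.05 carries a qualifier marking it as adjusted for sidedness, and the result sentence in the same section spells out the two-sided equivalent. Reading it as two-sided 0.05 means ignoring both. Judging the primary comparison at the level for which it was sized is what an analyst would do without further instruction.

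The 68% figure is therefore power at a level the plan does not adopt, not a shortfall in the plan. Two-sided 0.10 is lenient, and some statisticians would prefer 0.05. But with the same patients that choice cuts power for a 2-point difference from 80% to 68%, and restoring it means enrolling more. Reasonable statisticians would differ on that trade, and nothing in the document requires either side of it.

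**Conclusion.** The concern does not call for a change. The sample size section is internally consistent: 0.05 per tail is two-sided 0.10, and at that level 14 completers give 80.2% power and 17 give 87.2%. No stated rule or number is wrong.

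The residue is missing detail. The analysis section does not restate the level for the primary test. Carrying two-sided 0.10 over from 6.4.4, with a matching 90% confidence interval, gives a valid analysis and keeps the stated power. A report that gives the p-value, the level and its sidedness lets a reader who prefers 5% apply that standard.

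The figures assume a t-based crossover analysis with N − 2 degrees of freedom, a within-patient SD of 2 and a true difference of 2 points. With N − 1 degrees of freedom the power at 14 completers is 80.5% and 68.7%, which leaves the conclusion unchanged. The conclusion also assumes that the level is settled before unblinding. Choosing it after seeing a p-value between 0.05 and 0.10 would be a fault of conduct, and the plan's text gives no support for it.
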